#### 1.1. Background and rationale

Patient Decision Aids (PtDAs) are evidence-based interventions known to be effective in improving the quality of shared decision-making.

The CONNECT feasibility study is a cluster randomised controlled feasibility study with an embedded qualitative study. Eight clusters (NHS Trusts providing planned coronary angioplasty in England) will be recruited and randomised to the control or intervention arm at a 1:3 allocation ratio. Six clusters will implement a digital Patient Decision Aid 'CONNECT' and two clusters will provide usual care only. Questionnaires will be administered before and after delivery of intervention or control.

The overarching aim of this study is to determine whether it is feasible to conduct a cluster Randomised Controlled Trial (c-RCT) to test the effectiveness of CONNECT for improving shared decision-making for patients with stable angina.

The quantitative and qualitative data collected will enable us to assess:

- 1) the feasibility of delivering CONNECT in the planned coronary angioplasty patient pathway;
- 2) explore the acceptability of CONNECT to patients and cardiology teams;
- 3) assess the feasibility and acceptability of trial procedures.

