## 2. Study Methods

#### 2.1. Trial design

This is a two group, unblinded, multi centre, parallel cluster randomised controlled feasibility study with an embedded qualitative study. Clusters will be NHS Trusts that provide planned coronary angioplasty treatment for adults. Eight clusters will be recruited and randomised to the control or intervention arm at a 1:3 allocation ratio. Participants (n=320; 40 per cluster) will be patients with stable angina who are on the waiting list for planned coronary angioplasty or planned diagnostic coronary angiography with the potential to proceed immediately to treatment with coronary angioplasty ("angio query proceed"). Participants recruited from clusters in the intervention arm will receive the digital PtDA 'CONNECT'. Participants recruited from clusters in the control arm will

receive usual care. Questionnaires will be administered before and after delivery of intervention or control.

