#### 2.2. Randomisation

The eight Cardiology Departments are the units of analysis and will be randomised using stratified block randomisation with an allocation ratio of 3:1 to the intervention group and block size of four. Cardiology Departments will be stratified as appropriate, by factors such as the presence, or absence, of on-site surgical provision.

There will be no blinding, as the intervention will be delivered by the research nurse and cardiology teams. Randomisation will be conducted by the study statistician [name] and the statistician will conduct the randomisation blinded.

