## 3. Statistical Principles

#### 3.1. Confidence intervals and P-values

As the trial is a pragmatic parallel group RCT data will be reported and presented according to the CONSORT 2010 statement [8] and the CONSORT extension for pilot and feasibility studies [9]. As a pilot/feasibility study the main analysis will be mainly descriptive and focus on confidence interval estimation and not formal hypothesis testing. Results will be presented with their associated 95% confidence intervals. As this is a feasibility study and it's not powered to detect differences, P- values will not be used.

No methods for multiplicity adjustment will be used in this study.

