## 4. Analysis

#### 4.1. Analysis methods

As this is a feasibility study the main analysis will be predominantly descriptive and focus on confidence interval estimations rather than formal hypothesis testing. The baseline demographics and clinical characteristics of the patients will be reported overall and by randomised group. For the continuous variables (e.g., age) either mean and SD will be presented or median and inter quartile range (IQR) depending on the distribution of the data. The number of observations used in each calculation will be presented alongside the summaries.

We will look at differences between groups for the anticipated primary outcome (Decisional Conflict Scale). A random effects model (or another appropriate method) will be used to estimate the difference between the two treatment groups adjusting for age, sex, health literacy score, living alone, health burden (number of co-morbidities) and baseline decisional conflict scale score as fixed effects and hospital as a random effect to account for clustering. This difference and its associated 95% confidence interval will be used to check that the likely effect is within a clinically relevant range (as confirmation that it is worth progressing with the full trial) and to inform the sample size calculation for the definitive study as outlined previously. Similar analyses will be conducted for other secondary endpoints.

For the anticipated primary outcome (Decisional Conflict Scale) at follow up, the ICC for patients treated with the same site will be estimated using a marginal or random effects model.

The mean/median for anticipated primary and secondary outcomes (e.g. Coronary Angioplasty Knowledge questionnaire) at baseline and post-pre-assessment (along with its variability) will be reported for all participants.

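### SAP 4.1 gives no small-sample method for the 6-versus-2-site Decisional Conflict Scale contrast, so its 95% confidence interval can be too narrow

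*SAP*

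**What the plan says.** SAP 1.1 fixes the design: "Six clusters will implement a digital Patient Decision Aid 'CONNECT' and two clusters will provide usual care only". SAP 2.1 sets 40 patients per cluster, 320 in all. SAP 2.2 randomises by "stratified block randomisation with an allocation ratio of 3:1 to the intervention group and block size of four", and adds: "Cardiology Departments will be stratified as appropriate, by factors such as the presence, or absence, of on-site surgical provision".

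SAP 4.1 gives the analysis of the anticipated primary outcome: "A random effects model (or another appropriate method) will be used to estimate the difference between the two treatment groups". The model adjusts for age, sex, health literacy score, living alone and number of co-morbidities, together with "baseline decisional conflict scale score as fixed effects and hospital as a random effect to account for clustering". All six fixed effects are patient-level.

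SAP 2.4 adopts a precision framework. SAP 3.1 drops P-values and says "Results will be presented with their associated 95% confidence intervals". SAP 4.1 gives the interval for the arm difference two uses: checking that the likely effect lies in a clinically relevant range, as confirmation that the full trial is worth pursuing, and informing the definitive sample size.

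Neither document states REML or ML, a degrees-of-freedom method, a small-sample correction or a cluster-level analysis. Protocol 12.2 leaves the detail to the SAP. SAP 4.5 names R without a routine, and SAP 4.1.1 plans no sensitivity analyses.

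**The concern.** Arm is allocated by site, so the arm difference is a contrast between site means with 8 − 2 = 6 degrees of freedom, however many patients each site recruits. A large-sample (Wald z) interval treats the between-site variance as known. Here it is estimated from eight sites, and only two of them are controls.

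With no P-values, the interval is the inferential result. If it is too short, it overstates what eight sites can show about the size of the effect, and SAP 4.1 uses it in the judgement on progressing.

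A smaller, related issue concerns proportions such as adherence and retention. They come from the same sites, and the general promise of 95% intervals in SAP 3.1 makes no allowance for clustering.

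**Working it through.** **1. The plan's own figure.** The documents give no width or coverage for the eight-site model. The nearest figure is the full-trial size in SAP 2.3.2: 24 to 42 clusters and 914 to 1618 patients, for ICC 0.05, effect size 0.4 to 0.3, 90% power, two-sided 5% and average cluster size 40.

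- N = 4 × ((1.960 + 1.282)/d)² × DE, with DE = 1 + ((CV² + 1) × 40 − 1) × 0.05.
- The coefficient of variation (CV) of cluster size is not stated. Assuming 0.5, DE = 1 + (1.25 × 40 − 1) × 0.05 = 3.45.
- d = 0.4: N = 906, or 22.7 clusters, rounded up to 24 for equal arms. d = 0.3: N = 1611, or 40.3 clusters, rounded up to 42.

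The cluster counts reproduce and the patient totals are within 1%. ICC 0.05 is therefore the plan's working value; 0.01 to 0.10 is used below as a range.

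**2. Interval width with the variance known (total SD 1).**

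- SE = √[(1/6 + 1/2) × (ICC + (1 − ICC)/40)].
- At ICC 0.05: √[0.6667 × (0.05 + 0.02375)] = 0.2217.
- z: 1.960 × 0.2217 = ±0.43 SD. t on 6 df: 2.447 × 0.2217 = ±0.54 SD.
- 1.960/2.447 = 0.80, so z is 20% narrower. 2.447/1.960 = 1.25, so t is 25% wider.
- Analytic check: P(|t₆| < 1.96) = 0.902.

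**3. Coverage by simulation.** Eight sites of 40 split 6:2, random-intercept model, between-site variance truncated at zero, no patient covariates, 15,000 runs per setting:

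| Nominal 95% interval | ICC 0.01 | ICC 0.05 | ICC 0.10 |
|---|---|---|---|
| REML, z | 93.6% | 91.1% | 90.0% |
| ML, z | 92.1% | 87.4% | 85.6% |
| REML, t on 6 df | 97.8% | 95.9% | 94.9% |

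A run of 300,000 at ICC 0.05 gave 90.9% (REML-z), 87.3% (ML-z), 77.0% (uncorrected sandwich with z) and 95.0% (cluster-level t on 6 df).

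**4. Leaving out the stratification factor.** Same simulation at ICC 0.05, assuming two strata of four sites, each split 3:1:

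| Stratum effect | REML-z, stratum omitted: coverage (mean width) | REML-z, stratum in model | REML, t on 5 df, stratum in model |
|---|---|---|---|
| 0 | 91.1% (0.84 SD) | 90.4% (0.84 SD) | 96.2% (1.10 SD) |
| 0.3 SD | 94.4% (1.00 SD) | 90.0% (0.84 SD) | 95.9% (1.10 SD) |
| 0.5 SD | 98.1% (1.23 SD) | 90.2% (0.83 SD) | 96.1% (1.09 SD) |

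Omitting a prognostic stratum leaves its variance in the site term and widens the interval. Adding the stratum without a degrees-of-freedom correction returns coverage to about 90%.

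**5. Proportions.** Take 60% adherence among 6 × 40 = 240 intervention patients.

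- Simple binomial: 1.960 × √(0.24/240) = ±6 points.
- With clustering: 2.571 × √(0.24 × DE/240), where DE = 1 + 39 × ICC and t has 5 df.
- ICC 0.01 (DE 1.39): ±10 points. ICC 0.05 (DE 2.95): ±14. ICC 0.10 (DE 4.90): ±18.

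The documents give no ICC for adherence, so this range is an assumption.

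**The case against.** The strongest reply is that this is a feasibility study, explicitly unpowered, with a plan that leaves room for a suitable method. Four parts of that reply stand.

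- **A reader might infer that the intervals are bound to be too narrow.** The documents do not support that. SAP 4.1 fixes no interval method and allows an alternative, protocol 12.2 asks for methods appropriate to the design, and some R routines apply a degrees-of-freedom correction. It is a risk left open by the wording.
- **A reader might infer that omitting the stratification factor also narrows the interval.** Step 4 shows the reverse if the factor is prognostic, and this can mask the degrees-of-freedom problem. Nor is on-site surgery established as the factor: SAP 2.2 offers it only as an example.
- **A reader might take 77% as the coverage of the planned analysis.** The SAP names a marginal model only for estimating the ICC. A sandwich interval for the arm difference could enter only through the alternative-method clause.
- **A reader might infer that traffic-light results would change.** The thresholds in SAP 4.1.1 are percentages or counts with no interval rule, so the width of an interval alters none of them.

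The practical effect is also limited. At ICC 0.05 both half-widths (0.43 and 0.54 SD) exceed the planning effect of 0.3 to 0.4, so an interval centred on that effect includes zero either way. SAP Table 1 uses the effect estimate alongside previous research.

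The reply does not remove the core point. Being unpowered excuses a wide interval, but not one labelled 95% that covers 87% to 91%, when that interval is used to confirm that a full trial is worthwhile.

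**Conclusion.** The point holds as a gap in specification with a measurable consequence. At the SAP's own ICC, an uncorrected interval loses about 4 (REML-z) to 8 (ML-z) percentage points of coverage. The loss with REML-z is about 1 point at ICC 0.01 and 5 points at ICC 0.10. This rests on equal sites of 40, no patient covariates and a random-intercept model.

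Two lesser points go with it. Simple binomial intervals for patient-level proportions would overstate precision, by an amount that depends on an assumed ICC. The stratification factor is undefined and absent from the model; that is a mismatch between randomisation and analysis, and no cause of narrow intervals.

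The change should be made before analysis. It does not threaten the study's feasibility aims.

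**What to change.** In SAP 4.1:

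1. Specify REML with Kenward-Roger or Satterthwaite degrees of freedom, or a cluster-level analysis with t on 6 df. Exclude ML-Wald intervals and uncorrected sandwich intervals for the arm difference.
2. Name the factor actually used to stratify the randomisation and state whether it enters the model. This is a judgement: it costs one of six cluster degrees of freedom, and the t multiplier rises from 2.45 to 2.57 (2.571/1.960 = 1.31, so 31% wider than z on the same standard error). It should not be added without the degrees-of-freedom correction.
3. Where 95% intervals are given for patient-level proportions such as adherence and retention, allow for site, for example by using site-level rates with t on the number of sites minus one.

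The cost is SAP wording and standard R packages. The arm-difference interval becomes about 25% wider than with z. REML with t on 6 df is somewhat conservative (about 98% coverage) if the ICC is near 0.01.

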6.2. Randomisation

The eight Cardiology Departments are the units of analysis and will be randomised using stratified block randomisation with an allocation ratio of 3:1 to the intervention group and block size of four. Cardiology Departments will be stratified as appropriate, by factors such as the presence, or absence, of on-site surgical provision.

Details of the Cardiology Departments in England that have expressed an interest in participating in the study through the submission of an Expression of Interest document will be recorded. A separate linkage file will be developed by the Chief Investigator or delegate (Co-Lead, Research Fellow) in which each Cardiology Departments will be anonymised through the allocation of a unique identifier. In this way the identity of participating Cardiology Departments will be blinded to the study statistician, who will generate the allocation sequence (computer generated random numbers) and implement it.

The allocation ratio was chosen to maximise the number of clusters in the intervention arm to test the feasibility, practicality, and acceptability of the intervention. A control arm was included to evaluate the feasibility and acceptability of trial procedures such as the willingness of Cardiac Departments to be randomised. This study is not a 'mini-version' of the future c-RCT designed to test the effectiveness of the intervention.

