12.2 Quantitative data analysis

As this is a feasibility study the main analysis will be predominantly descriptive and focus on confidence interval estimations rather than formal hypothesis testing. The baseline demographics and clinical characteristics of the patients will be reported overall and by randomised group. For the continuous variables (e.g., age) either mean and SD will be presented or median and inter quartile range (IQR) depending on the distribution of the data. The number of observations used in each calculation will be presented alongside the summaries. We will look at differences between groups for the anticipated primary outcome (Decisional Conflict Scale) using analysis methods appropriate to the design of the study. Analysis will be described in detail in the Statistical Analysis Plan. This difference and its associated confidence interval will be used to check that the likely effect is within a clinically relevant range (as confirmation that it is worth progressing with the full trial) and to inform the sample size calculation for the definitive study as outlined previously. The mean/median anticipated secondary outcomes (Coronary Angioplasty Knowledge questionnaire) at baseline and post-pre-assessment (along with its variability) will be reported for all participants. For the anticipated primary outcome (Decisional Conflict Scale) at follow up, the ICC for patients treated with the same site will be estimated using a marginal or random effects model. Details of the 'Stop'/'Change'/'Go' criteria derived from data collected in this feasibility study will determine progression to a future large-scale evaluation (c-RCT).

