#### 2.3. Sample size

#### 2.3.1.Pilot trial sample size

From each cluster a non-probability sample of 40 consecutive patient participants (320 in total) will be recruited. A formal power calculation is not required for a feasibility study as testing intervention effectiveness is not the aim. However, the sample size should be sufficient to estimate the uncertain critical parameters: Standard Deviation (SD) of the primary outcome, recruitment/consent rates, ICC and the average cluster size needed to inform the design of the future full-scale c-RCT with sufficient precision. A minimum of 8 clusters in total is needed to best estimate the ICC [2]. Using Swiger's formula for the variance of the ICC [3], the precision gain of the ICC estimate diminishes after 30-50 patients per cluster. As more clusters with fewer patients is preferred, an average of 40 patients from each cluster will be recruited, leading to a total sample of 320 patients. Allowing for a median consent rate of 70% [4], a total of 457 patients will be approached to participate, approximately 57-58 per cluster. This sample size will be efficient to estimate the feasibility outcomes.

On average, each cluster will have 5-10 cardiologists, who will see about 400-1000 patients per year. Approximately 30,500 patients per year have planned CA for stable angina. There are 98 UK NHS cardiac centres that perform CA. This suggests, on average, 312 patients are eligible per cluster. Accounting for a median consent rate of 70% [4], 218 patients could be consented in one year. Therefore, 40 patients per cluster within 12 months should be feasible.

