Intra-cluster Correlation Coefficient (ICC) and sample size calculation for full scale c-RCT	
 
Estimate of the ICC of the Decisional Conflict Scale at T2 using a marginal or random effects model.
 
The full c-RCT sample size will be calculated based on estimates of the effect size (alongside previous research), the standard deviation and the ICC from the anticipated primary outcome analysis.
 

Practicality of implementing CONNECT in NHS settings	
 
CONNECT implementation:         
 
Number of participants who access CONNECT.
 
Percentage of pre-assessment clinic visits in which the CONNECT summary was used during the consultation.
 
Qualitative analysis of training session minutes and interview transcripts to summarise:                 
 
Potential variations in usual-care patient pathway for planned coronary angioplasty.
 
Practicalities of providing a digital PtDA in the NHS.
 
Barriers and enablers to integrating the CONNECT summary.
 
 
 

Reasons for non- consent to study participation	Qualitative analysis to summarise: • Reasons for Cardiology Departments nonparticipation. • Reasons for patient nonparticipation.

Uncertainty	Outcomes
Acceptability of	Qualitative analysis of interviews to explore:
CONNECT and study procedures	
 
Self-reported adherence to CONNECT and how it was used by patients at home and during the pre-assessment clinic.
 

	
 
Barriers and enablers to recruitment and using CONNECT at home and during pre-assessment clinic.
 

	
 
Understanding, appropriateness, and potential burden of questionnaire completion.
 

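### The between-arm DCS difference from six versus two clusters is too imprecise to confirm that the full trial is worth running or to inform its size

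*SAP*

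**What the plan says.** SAP 4.1 fits a random effects model to the DCS and says of the adjusted difference between arms: "This difference and its associated 95% confidence interval will be used to check that the likely effect is within a clinically relevant range". It gives the purpose as "as confirmation that it is worth progressing with the full trial) and to inform the sample size calculation for the definitive study". Protocol 12.2 gives the same reason: "as confirmation that it is worth progressing with the full trial". SAP Table 1, repeated in protocol Table 2, adds: "The full c-RCT sample size will be calculated based on estimates of the effect size (alongside previous research), the standard deviation and the ICC".

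Other parts of the plan point away from this use.

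- Protocol 1.3.2 says the study is not powered for the future primary outcome.
- Protocol 6.2 says it is not a small version "of the future c-RCT designed to test the effectiveness of the intervention", and explains the 3:1 allocation by the wish to test the intervention's feasibility.
- SAP 2.3.1 (and protocol 12.1.1) lists what the sample must estimate to "inform the design of the future full-scale c-RCT with sufficient precision": the SD, recruitment and consent rates, the ICC and the average cluster size. The between-arm effect is not on the list.
- The progression table in SAP 4.1.1 has no row for the size of the effect, and neither document defines the clinically relevant range.

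**The concern.** The plan disclaims effectiveness and then gives the effectiveness estimate two jobs: supporting the decision to go on, and feeding the sample size of the definitive trial. Only two clusters carry the control arm, so the interval may be too wide for either.

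A check that a useless decision aid would usually pass gives false reassurance. Because no range or pass rule is fixed in advance, it would also be interpreted after the results are known. On sizing, the required number of patients varies with the inverse square of the effect, so ordinary sampling error in the pilot estimate becomes a several-fold error in trial size if that estimate carries much weight. Nothing in the plan limits its weight.

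**Working it through.** **Inputs.** Six intervention and two control clusters (SAP 1.1); 40 patients per cluster (SAP 2.1); ICC 0.05, target effect 0.3 to 0.4 SD, 90% power, two-sided 5%, average cluster size 40 (SAP 2.3.2). Effects are in SD units, with benefit counted as positive.

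**1. The SAP's own full-trial figure.** Patients per arm = 2 × (1.960 + 1.282)² / d², which is 234 for d = 0.3 and 132 for d = 0.4. The design effect is 1 + [(1 + CV²) × 40 − 1] × 0.05. The SAP allows for variable cluster size but gives no CV.

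- Equal clusters: design effect 2.95; 468 × 2.95 = 1,381 and 264 × 2.95 = 779. These do not match.
- CV 0.5 (assumption): design effect 3.45; 468 × 3.45 = 1,615 and 264 × 3.45 = 911. Divided by 40 and rounded up to an even number, these give 42 and 24 clusters.

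The SAP states 914 to 1618 patients in 24 to 42 clusters, so its figures are reproduced.

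**2. Precision of the pilot difference.** Variance = (ICC + (1 − ICC)/m) × (1/6 + 1/2). At ICC 0.05 and m = 40 this is (0.05 + 0.95/40) × 0.6667 = 0.0492, so SE = 0.222 SD. The 95% half-width is 2.447 × 0.222 = 0.54 SD (t on 8 − 2 = 6 df) or 1.960 × 0.222 = 0.43 SD (normal). At a true 0.35 SD the expected t interval runs from about −0.19 to 0.89.

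**3. The check when CONNECT has no effect.** With no pass rule stated, I take a pass to mean that the interval reaches 0.3 SD. The normal version is P(Z ≥ 0.3/SE − 1.960). The t version, with the SE itself estimated on 6 df, is the chance that a non-central t with non-centrality −0.3/SE exceeds −2.447.

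| Scenario | SE | Half-width, t | Passes under no effect, t | Normal |
|---|---|---|---|---|
| ICC 0.05, 40 per cluster | 0.222 | 0.54 | 79% | 73% |
| ICC 0.01 | 0.152 | 0.37 | 62% | 50% |
| ICC 0.10 | 0.286 | 0.70 | 86% | 82% |
| ICC 0.05, 32 analysed per cluster (80% retention) | 0.230 | 0.56 | 80% | 74% |
| ICC 0.05, covariates remove half the variance (assumption) | 0.157 | 0.38 | 64% | 52% |

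If the bar is 0.4 SD instead, the first row gives 67% (t) and 56% (normal). At a true 0.35 SD, the t interval reaches 0.3 in 98% of studies. The comparison is therefore 98% passing when the aid works with 79% when it does not.

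If a pass required the interval to exclude zero, it would occur in only about 21% of studies at a true 0.3 SD and 33% at a true 0.4.

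**4. The estimate as a sizing input.** At a true 0.35 SD and SE 0.222:

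- P(0.3 < estimate < 0.4) = P(|Z| < 0.05/0.222) = 18%.
- P(estimate ≤ 0) = P(Z < −0.35/0.222) = 6%.

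If an estimate one SE low (0.128) or high (0.572) were used alone, the formula in step 1 with CV 0.5 would give about 8,800 or 450 patients, against the SAP's 914 to 1618.

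**5. The ICC (secondary).** Swiger's variance with k = 8, n = 40, N = 320 and ICC 0.05 is 2 × 319 × 0.95² × 2.95² / (40² × 312 × 7) = 0.00143, so the SE is about 0.038, three quarters of the ICC itself.

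**The case against.** A reader might infer that a low estimate would stop the programme. The documents do not support that. Progression is tied to the table in SAP 4.1.1, which has no effect criterion; the check in SAP 4.1 has no threshold and no red outcome. It is an undefined extra test alongside the agreed criteria.

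A reader might also infer that the pilot estimate alone will size the full trial. The text says it will inform the calculation, and SAP Table 1 sets it beside previous research; SAP 2.3.2 already holds external values of 0.3 to 0.4 SD. The figures of 8,800 and 450 are therefore the extreme case. What remains is that no rule limits the pilot's share.

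Nor is the check worthless in every study. In the base case about 21% of null studies (t) or 27% (normal) would exclude 0.3 SD. A lower ICC or strong covariates would improve on that, and the model does adjust for baseline DCS and five other covariates. Point estimates below 0.3 SD when the truth is 0.35 also prove little: a definitive trial with 90% power for 0.35 SD (SE 0.108) would give them 32% of the time.

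The precision framework (SAP 2.4) and the absence of P-values (SAP 3.1) do not answer the point, because the interval itself is the tool for the check. The allocation is not the root cause either: four versus four clusters would still give a half-width of 0.47 SD.

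On the ICC, SAP Table 1 already takes it from the primary outcome analysis, whose model includes arm, and SAP 3.1 already promises 95% intervals. Only its use at a single value needs attention.

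**Conclusion.** The concern stands as a fault in how the estimate is to be used, not in the feasibility design. At the SAP's own ICC, cluster size and allocation, the 95% half-width of 0.54 SD (normal: 0.43) exceeds the whole target effect of 0.3 to 0.4 SD. Over ICC 0.01 to 0.10 the t half-width runs from 0.37 to 0.70 SD. A useless aid would pass the check, read as the interval reaching 0.3 SD, in about 79% of studies, and in 50% or more in every scenario tabulated. The check discriminates poorly, though not at all levels of ICC equally, and the estimate is a poor input to sizing.

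The assumptions are equal clusters of 40 in the pilot, t on 6 df (the SAP names no small-sample method), no covariate gain in the base case, and my reading of a pass. The CV of 0.5 affects only the full-trial sizes. The documents do not support reading this as a formal stop rule on the effect, or as sizing from the pilot alone.

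**What to change.** 1. In SAP 4.1 and protocol 12.2, delete the clinically-relevant-range check as confirmation for progressing. Report the DCS difference and its 95% interval descriptively, and leave progression to the agreed table.
2. In SAP 4.1, SAP Table 1 and protocol Table 2, base the full-trial effect size on a pre-specified important DCS difference. The SAP already plans on 0.3 to 0.4 SD. Take only the SD and ICC from this study.
3. Secondary: show the full-trial size across the ICC's 95% interval and at the external value of 0.05, not only at the point estimate.

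The cost is wording in two documents. Data collection, recruitment and the agreed progression criteria are untouched. The one real loss is that the feasibility report no longer offers an effect signal in support of progression.
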